11.4 Measurement tools used

Data collection tools developed for this study have been based on previously used tools, including those recommended in the literature, including:

- ICHOM Pregnancy and Childbirth standard set (ICHOM, 2016) which includes questions relating to breastfeeding outcomes, maternal-infant attachment and maternal satisfaction (Dennis, 2003, Taylor et al., 2005);
- New Zealand First Days Pod evaluation tool (Cowan, 2016);
- Queensland Indigenous Pēpi-Pod® Program evaluations (Young, 2016; Young et al., 2016);
- Published breastfeeding evaluation tools, Breastfeeding Self-Efficacy Scale-Short Form (BSES-SF) (Dennis, 2003) and the Breastfeeding success variable (ICHOM, 2016);
- Queensland Nursing and Midwifery Knowledge, Attitudes and Practices relating to risk for SUDI (Young and Schluter, 2002; Young and O'Rourke, 2003; Young et al., 2008);
- Safe Sleep Education Project Survey and Practice Audit Tools (Young et al., 2010);
- Queensland Infant Care Practice Study (Schluter and Young, 2002; Young et al 2008).

Additional questions have been developed to address specific outcomes of this pilot where no pre-existing tool was available. Please see Table 1 for the outcomes that will be measured.

Table 1: Proposed outcome, measurement tool and time point of data collection

Outcome	Measurement tool	Time point	Person responsible
Maternal and neonatal demographic data	Client Health Record	≥ 36 weeks of gestation AND after birth	Research Assistant, Registered Midwife
Breastfeeding Method	Breastfeeding success variable (ICHOM, 2016)	≤ 3 days / prior to discharge (immediate rate) AND 6-8 weeks (medium rate) AND	Research Assistant, Registered Midwife

		4 months (long term rate)	
Breastfeeding self-efficacy	Breastfeeding Self-Efficacy Scale-Short Form (BSES-SF) (Dennis, 2003)	≤ 3 days / prior to discharge (immediate rate) AND 6-8 weeks (medium rate) AND 4 months (long term rate)	Research Assistant, Registered Midwife
Maternal acceptability of the SSD or control	Questionnaire (author developed)	≤ 3 days / prior to discharge	Research Assistant, Registered Midwife
Staff acceptability of the SSD or control	Questionnaire (author developed)	Approx. 16-20 weeks after study commencement	Research Assistant, Registered Midwife
Maternal-infant attachment	Mother-to-Infant Bonding Scale (MIBS) (Taylor et al., 2005, ICHOM, 2016)	≤ 3 days / prior to discharge AND 6-8 weeks AND 4 months	Research Assistant, Registered Midwife
Maternal satisfaction with the care received, elements of intervention (comfort, access to baby, impact upon sleep, settling, feeding)	Maternal Satisfaction Questionnaire (adapted ICHOM, 2016)	≤ 3 days / prior to discharge	Research Assistant, Registered Midwife
Delivery of culturally appropriate care	Demographic Questionnaire (author developed)	≤ 3 days / prior to discharge	Research Assistant, Registered Midwife
Accessibility of personal options and choice in care	Care Options Questionnaire (author developed)	≤ 3 days / prior to discharge	Research Assistant, Registered Midwife
Adverse events (e.g. baby falls from maternal beds or chairs)	PRIME, Client Health Record	≤ 3 days / prior to discharge	Research Assistant, Registered Midwife, Midwifery Unit Manager
Maternal consistency of practice with safe sleeping recommendations	Maternal Safe Sleep Awareness Questionnaire (Schluter & Young	≤ 3 days / prior to discharge AND 6-8 weeks AND	Research Assistant, Registered Midwife

	2002) AND Audit / compliance of Safe Sleep recommendations (Young et al., 2010)	4 months (sleep position, sleep location) Pre-Audit: 4 weeks prior to study commencing Post-test: ≤ 3 days / prior to discharge	
Staff consistency of practice with safe sleeping recommendations	Staff Safe Sleep Awareness Questionnaire and Chart Audit Tool (Young and Schluter 2002, Young et al., 2008)	Pre-test: 4 weeks prior to Phase One recruitment Post-test: Approx. 16-20 weeks after Phase One commencement	Research Assistant, Registered Midwife

11.5.1 Study involvement by mothers and infant participants

Phase 1: Pretest Infant Sleep Observation and Maternal Chart Audit

In liaison with maternity unit manager and shift coordinators for the postnatal unit, the research assistant will identify eligible mother-baby pairs for a) the maternal medical charts/nursing notes audit (n=100) and b) infant sleep period observations (n=100). Consent from mothers will be obtained prior to observed sleep periods and chart documentation. Chart and observational audits will be conducted with audit tools used in a previous study, which included safe sleeping outcomes in postnatal settings (Young et al., 2010). Audits will be conducted during a 4-6 week period prior to Phase 2, which involves recruitment with a second maternal sample.

An observational assessment (infant sleep observation) of participating infants nursed in the Postnatal unit (target n=100) will be conducted during which infant sleep position and infant sleep environment will be observed and documented using an audit tool that addresses infant sleep position and sleeping environment consistent with current safe sleeping messages e.g. baby placement in cot, bedding used and placement, presence of objects in cot. Based on the estimated number of births per month at this tertiary facility (approx 230/month with 10-15% admitted to special care nurseries) the target sample of audits is achievable during this 4 week period.

Audit inclusion criteria for infants will include all newborns admitted with their mothers to the postnatal unit, including those term and preterm infants who have recovered from acute respiratory distress; infants with reflux; and infants for whom sepsis for investigation has been ruled out. Infants with upper airway malformations such as Pierre Robin Syndrome will be excluded given their individualised positional needs that influence safe sleeping recommendations for the supine sleep position, depending on severity of the condition. The observational period will be conducted during an intended rest or sleep period for the infant, to ensure that allocated 'tummy play time' is excluded.

Maternal charts will be audited to determine staff documentation of care and discharge information provided to parents/caregivers about safe sleeping messages. An entry in the

maternal chart relating to parent education about safe sleeping messages will be coded as a positive entry.

Phase 2: Safe Sleep Devices

Once the mother has birthed, she will be randomly allocated on admission to the postnatal unit to the MaBim side-car crib, First Days Pēpi-Pod® or control (usual care with baby sleep space being independent hospital Perspex cot on wheels) during the postnatal stay.

All participants will be shown the Video Clip titled 'Safe, Sleep, Little One' (CFOC Ltd, 2016) by the midwife once orientated to the ward. If allocated to the First Days Pēpi-Pod, participants will also be asked to view the Picture Demonstration (CFOC Ltd, 2016). Participants allocated to the MaBim neonatal crib will be shown the MaBim Product Brochure. Those randomised to the control group (usual cot care) will receive standard care instructions.

Participants will be followed up by the Research Assistant during the hospital admission to assess breastfeeding rates, acceptability of the ISSD or control, maternal-infant attachment, maternal satisfaction with the care received, culturally appropriate care, accessibility of personal options and choice in care, adverse events (baby falls from maternal beds or chairs) and awareness of, and compliance with, safe sleeping recommendations. Participants will be asked to complete the questionnaires, expected to take thirty minutes of the participants' time. The participant will be given the choice to complete the questionnaires independently or have the Research Assistant read the questions. The questionnaire will be available online (Opinio Survey Software 7.1) and in paper format.

If participants discharge prior to contact with the Research Assistant, she will be contacted within seventy-two hours of discharge, or at the next time of convenience.

Prior to discharge, participants will be asked to view the 'Red Nose Safe Sleeping' information (SIDS and Kids Australia, 2016) available via the mobile phone application. This information video promotes safe sleeping practices in the home environment.

Infant sleep observation and maternal chart audits for participating mothers and babies will be conducted (using the audit tools described in Phase 1) prior to discharge.

Six to eight weeks after the birth, the participants will be contacted either by phone or email depending on individual preference. During this point of contact, breastfeeding rates, maternal-infant attachment, and safe sleeping practices, will again be assessed. Participants will be asked to complete the Questionnaires, which is expected to take ten to twenty minutes of their time. The questionnaire will be available online (Opinio Survey Software 7.1) and in paper format.

Four months after the birth, participants will be contacted to assess the way that they are feeding their baby at that time (to determine breastmilk feeds and breastfeeding rates), maternal-infant attachment and safe sleeping practices. The questionnaire will be available online (Opinio Survey Software 7.1) and in paper format. This questionnaire is expected to take expected to take ten to twenty minutes of their time.

Participants will not receive any financial compensation for participation in this study.

The safe sleep enabler study protocol will be implemented and mother and baby recruitment is expected to take approximately 4-6 months.

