5.2 Secondary Hypotheses

This study has several secondary hypotheses, due to the need to pilot a protocol and identify key outcomes for a larger, randomised controlled trial. Secondary hypotheses include:

1. Maternal satisfaction with infant safe sleep enablers will be demonstrated by mothers in the maternity unit setting.
2. Staff who use the infant safe sleep enablers will find infant safe sleep enablers acceptable to use in practice in the maternity unit setting.
3. Mothers who use a safe sleep enabler for their infant in the postnatal unit will report higher levels of satisfaction with care, maternal-infant attachment outcomes, breastfeeding rates, and safe sleeping awareness during the postnatal period (≥ 3 days and 6-8 weeks) compared to mothers who use the current standard cot and separate maternal bed.
4. Mothers who use a safe sleep enabler for their infant in the postnatal unit will report higher breastfeeding rates and safe sleeping awareness at 4 months postnatal age compared to mothers who use the current standard cot and separate maternal bed.
5. Mothers who use a safe sleep enabler for their infant in the postnatal unit will report the same or reduced length of hospital stay, and the same or lower rate of adverse events including baby falls during hospitalisation.
6. Compared to pretest knowledge, attitudes and self reported practices, staff will demonstrate an improvement in knowledge, attitudes and self reported practices consistent with current safe sleeping recommendations and known risk factors at the conclusion of the pilot period.
7. Compared to pretest audits of infant sleep position, environment and documentation of parent education, there will be an improvement in practices and documentation processes consistent with current safe sleeping recommendations and known risk factors at the conclusion of the pilot period.

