Staff Survey Data: Should continuous data be distributed symmetrically, then means and standard deviation (SD) will be reported. Medians, inter-quartile ranges (IQR), frequencies and percentages will be used to report the central tendency, spread and empirical distributions of categorical and non-symmetric continuous variables elicited at each survey. All bivariate comparisons of categorical frequencies will be undertaken using Fisher's exact test, log-linear and logistic models, while McNemar's test and Agresti's test of symmetry will be used to detect differences between participants' responses at any two survey points (pretest vs post-test). Continuous data will be analysed using Student's t-test, Student's paired t-test, ANOVA or using their nonparametric equivalents (should the data exhibit non-normality).

Audit data: All qualitative data will be coded prior to data entry. Frequency data will be reported and analysed using standard categorical techniques (accounting for the matched nature of the data between mother and baby). Univariate linear modelling will be conducted for dependent variables that will include infant sleep position, infant placement in the cot, placement and securement of bedding; and presence of particular objects in the cot, e.g. Infant quilts, toys, cot bumpers.

All statistical comparisons will be analysed using the SAS or SPSS statistical software package (IBM Corp 2013). A value of $p=0.05$ will be used to define statistical significance for primary outcomes as they are independent of each other. We recognize that there are a large number of secondary outcomes and will report uncorrected p values with a nominal level of significance of 0.05.

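### The before/after audit for secondary hypothesis 7 compares a broad ward sample with selected, video-briefed trial participants, so a difference cannot be read as changed ward practice

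*Protocol*

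**What the plan says.** Hypothesis 7 (Protocol, 5.2) reads: "Compared to pretest audits of infant sleep position, environment and documentation of parent education, there will be an improvement in practices and documentation processes" by the end of the pilot. The related outcome in 10.2 is set at unit level: how far safe-sleep recommendations are implemented on the postnatal unit.

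Section 11.5.1 describes two audits with the same tools.

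- **Phase 1 (before), target 100.** "Audit inclusion criteria for infants will include all newborns admitted with their mothers to the postnatal unit". Recovered preterm infants and infants with reflux are expressly included; upper airway malformations are excluded. "Consent from mothers will be obtained prior to observed sleep periods". No limit is set on feeding intention, plurality, maternal BMI or English. A chart entry on parent safe-sleep education scores as positive.
- **Phase 2 (after).** "Infant sleep observation and maternal chart audits for participating mothers and babies will be conducted", before discharge. These pairs are another group of mothers: Phase 2 is the phase "which involves recruitment with a second maternal sample". Sections 9.1 and 9.2 define them.

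Between admission and the Phase 2 audit, "All participants will be shown the Video Clip titled" is followed by the name of a safe-sleep clip, and the control arm is included. Participants are also asked to view further safe-sleep information before discharge.

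Table 1 (11.4) also lists a staff chart audit with a post-test at about 16 to 20 weeks, without naming its population.

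For the audit data, 12.2 names categorical techniques and then adds: "Univariate linear modelling will be conducted for dependent variables that will include infant sleep position", together with cot placement, bedding and objects in the cot.

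**The concern.** A before/after audit can speak to ward practice only if the two samples are alike apart from time. Here they differ in who is sampled, in what the mothers have been shown, and for many pairs in the sleep space itself. Several audit items describe exactly that space: placement in the cot, bedding and objects.

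Documentation is exposed too. If midwives chart the trial video as parent education, the documentation rate rises because a trial procedure was recorded, even if routine education has not changed.

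At stake is a wrong claim that the unit improved. It would have a practical reader, because 12.1 says the baseline audit also serves monitoring under the state guideline. Who is audited, and what is recorded in Phase 1, is fixed by the protocol. A later analysis plan cannot restore eligibility items that were never collected.

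**Working it through.** **The two samples side by side**

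| | Phase 1 audit | Phase 2 audit |
|---|---|---|
| Source | Newborns rooming in on the unit, with consent | Trial participants |
| Feeding | No limit | Intending to breastfeed |
| Plurality | No limit | Singleton |
| Maternal BMI, English | No limit | Below 40; reads English |
| Infant | Recovered preterm and reflux included; airway malformations excluded | No immediate SCN/NICU admission, phototherapy or CPAP |
| Trial video | No | All arms |
| Sleep space | Usual cot | Standard cot, Pēpi-Pod or MaBim |
| Number | 90 to 100 (12.1) | 90 (12.1) to 180 (11.3) |

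**How many Phase 2 pairs are in the usual cot.** Equal allocation of 180 gives 60 per option. Under 11.3, a pair whose device is in use gets a standard cot and forms a fourth group. The mock run there expects about half of the MaBim allocations to be met. If Pēpi-Pods never run out (assumed), standard cots hold 60 + 30 = 90 of 180 pairs. If no device is ever unavailable, they hold 60. So the range is about 60 to 90 pairs, with 90 to 120 in devices.

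**Size of the possible artefact.** The plan gives no compliance rate, effect size or power for the audit, so there is no figure to reproduce. All rates below are assumptions. Inputs: 100 pairs before, 90 or 180 after, two-sided 0.05 (the level is in 12.2; two-sided is assumed), trial-eligible pairs 70% compliant, usual ward care unchanged.

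Chance of a significant rise = Φ[(Δ − 1.96·SE₀)/SE₁], where SE₀ uses the pooled proportion and SE₁ the separate ones.

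Example, video adds 10 points, 90 after:
- pooled proportion = (70 + 72)/190 = 0.747
- SE₀ = √[0.747 × 0.253 × (1/100 + 1/90)] = 0.0631
- SE₁ = √(0.21/100 + 0.16/90) = 0.0623
- Φ[(0.10 − 0.1237)/0.0623] = Φ(−0.381) = 0.35

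Case-mix shift = (ineligible share of Phase 1) × (compliance gap). With 20% to 40% ineligible and 50% to 60% compliant, it runs from 0.20 × 10 = 2 to 0.40 × 20 = 8 points.

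| Scenario | 90 after | 180 after |
|---|---|---|
| No bias | 2.5% | 2.5% |
| Case mix only, +2 to +8 points | 5% to 21% | 5% to 28% |
| Video only, +10 points | 35% | 47% |
| Video only, +20 points | 94% | 98% |
| Case mix and video +10 | 47% to 78% | 61% to 90% |

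The sign of the case-mix rows is assumed. If ineligible pairs complied better, the same formula would give a fall of 2 to 8 points.

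**Linear model.** Exact enumeration with no true change, 100 before and 90 or 180 after, compliance 0.5 to 0.95: two-sided type I error is 0.049 to 0.056 for linear regression on a 0/1 item, and 0.049 to 0.056 for chi-squared.

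**The case against.** The other side has real points.

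- *Hypothesis 7 does not say that staff alone caused the change.* The video and briefings can be seen as part of the pilot package. That is fair, and it is why the remedy is partly a statement of what the contrast contains. But the unit-level outcome in 10.2 invites the reading as ward practice, and the package reached participants only.
- *Phase 1 is not literally every newborn.* It needs consent and excludes airway malformations, and its infants are on the unit with their mothers, which narrows the special-care difference. This stands. The differences in feeding intention, plurality, BMI, English and briefing remain.
- *The 16 to 20 week chart audit may give documentation another comparison.* Possibly, but its population is not stated. The only post-test sleep observation described in 11.5.1 is of participants.
- *It is one secondary hypothesis in a pilot, with uncorrected p values.* True, and it limits the weight of the point.

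Three stronger readings are tempting and are not supported:

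- *Case mix favours improvement.* The documents do not show this. Sections 1 and 2 link breastfeeding with bed-sharing, so restriction to breastfeeding mothers could lower observed compliance on sleep location.
- *Two thirds of participants sleep in a device, leaving only about 60 in standard cots.* This overlooks the reallocated fourth group in 11.3.
- *Linear models manufacture a false improvement.* The error rate stays near 5%, and 12.2 also names categorical techniques.

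**Conclusion.** The point holds as a mismatch of design. The two audits sample different populations, and the second has received trial-only safe-sleep education before it is measured. A difference cannot separate ward practice from selection, briefing and device.

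The briefing is the one component with a clear direction, towards apparent improvement, including through chart entries. Its size is not in the documents. Under the assumed 10 to 20 points, it alone gives a 35% to 98% chance of a significant rise. The case-mix effect is likely smaller under the ranges tried, and its direction is unknown.

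No primary outcome and no randomised comparison depends on this, so it is a worthwhile, inexpensive improvement and not a threat to the pilot.

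The modelling point is separate and minor. A linear model does not suit an unordered item such as sleep position, and 12.2 does not say how it relates to the categorical techniques.

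**What to change.** 1. Before Phase 1 starts, add the Phase 2 eligibility items to the audit form: feeding intention, plurality, BMI, English, gestation, SCN/NICU admission, phototherapy or CPAP.
2. Make the main before/after contrast trial-eligible Phase 1 pairs against Phase 2 pairs in standard cots. Show those randomised to the standard cot and those reallocated to it separately.
3. Report device users separately.
4. State in 5.2 and 12.2 that the contrast includes the trial video and briefing.
5. State in Table 1 which population the 16 to 20 week chart audit covers.
6. Separately, in 12.2 replace univariate linear modelling with logistic models for binary items and a multinomial model for sleep position. Report differences in proportions with 95% confidence intervals.

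The cost is a few form fields, protocol wording and precision. At 70% compliance (assumed), the 95% half-width is 1.96 × √[0.21 × (1/100 + 1/180)] = 11 points for all pairs. With 60 to 80 eligible Phase 1 pairs (assumed) it becomes 1.96 × √[0.21 × (1/80 + 1/90)] = 14 points with 80 against 90 pairs, and 1.96 × √[0.21 × (1/60 + 1/60)] = 16 points with 60 against 60.

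These steps do not remove the video effect. If a statement about the whole ward is wanted, a post-audit under the Phase 1 criteria that includes non-participants, reported by participation, would be needed. Section 16 prices 100 sleep observations with consent at 25 hours and $1,466.75 in labour, which indicates the cost of the observation part.

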11.5.2 Study involvement by staff

Nurses and midwives, the primary health professionals in contact with parents of young infants, have a key role in reducing the incidence of SUDI. This part of the study aims to determine postnatal nursing and midwifery staff perceptions of the acceptability of the safe sleep intervention and its impact on clinical practice and staff awareness of safe sleep recommendations.

The Staff Study (Phase 3) will use a pre-test post-test intervention design conducted in two parts. The sample of nurses and midwives involved in the care of infants and their families will include all eligible staff in the postnatal unit (approx. target n=80).

Staff Orientation to Protocol (Phase 2)

Phase 2: Staff Orientation to Safe Sleep Enablers and RCT Protocol

In collaboration with ward managers in the participating clinical areas, the Investigators and Research Assistant will negotiate appropriate days and times to conduct the orientation to the new safe sleep enablers, including safety briefing and set-up with postnatal ward staff. The study protocol will be explained in detail with written information provided and reminder sheets provided in mutually agreed sites in the participating sites. The protocol briefing will include consent process, randomisation process, documentation, and research team contact information. All team leaders will be briefed in order to ensure they are able to support staff.

Phase 3: Staff Knowledge, Attitudes and Practices

Part 1: Pre-test Knowledge, Attitudes and Practices Staff Questionnaire

[figure not shown]
The Research Assistant will identify participants meeting the inclusion criteria from the unit roster in liaison with the Maternity Unit Manager of the postnatal unit (target n=80). All identified enrolled, registered nurses and midwives practicing in this unit will be approached to participate in the pretest survey. The survey and participant information sheet will be delivered to participants at their mail point in the postnatal unit in Phase 1. The Staff safe sleeping survey will take approx. 15-20 minutes of the participant's own time to complete. Participants will return the form by sealed collection box available on the unit or by Opinio Survey Software (Opinio 7.1, ObjectPlanet, Inc.) using a specific code. Surveys will be numerically coded to allow one reminder notice to be sent for failures to return, two weeks after the original distribution. This numerical code will also facilitate matching of pretest (prior to trial) and post-test 1 (4-5 months' post commencement) staff surveys. Initial distribution will occur approximately 6 weeks prior to Phase 2 commencing.

Part 2: Post-test Knowledge, Attitudes and Practices Staff Questionnaire

[figure not shown]
The post-test survey is identical in content to the pretest with the addition of questions relating to staff perceptions of the infant sleep spaces available for parents on the ward to use. This survey is anticipated to take 20 minutes to complete. This questionnaire will be conducted at the commencement of the 4-5th month after the trial has begun to allow familiarity with procedures. A four week return period with reminders at staff handovers will be provided.

Reminders to complete questionnaires will be given in staff meetings and shift handover periods through liaison of the researchers with departmental managers. One reminder notice and survey will be sent to each participant who does not return the survey form within 2 weeks of receiving it. It is anticipated that a minimum of 65-70 nurses and midwives will be recruited based on previous participant response rates.

[figure not shown]
The below flow chart demonstrates the study involvement of participants Phase 1:

The below flow chart demonstrates the study involvement of mother and infant participants Phase 2:

The below flow chart demonstrates the study involvement of staff participants Phase 3:

